1.4 Relevant Literature and Data

The studies similar to that being conducted here have been conducted before (Table 1, Figure 1). The only difference is that we are using a set of 10 genotypes instead of individual genotypes that were used in studies before.

2 STUDY OBJECTIVE

2.1 Our goal for this study is to generate preliminary data that is needed to support an application to NIH for funding of a larger, adequately-powered study to explore whether a set of genotypes, that increase the risk for nonalcoholic fatty liver disease (NAFLD), predispose individuals to increased *de novo* lipogenesis (DNL) and liver fat accumulation when exposed to fructose intake.

2.2 Primary Objective: To explore the genetic-specific effects of fructose on liver fat accumulation using MRI

2.3 Secondary Objective: To explore the genetic-specific effects of fructose on markers of liver fat accumulation (fibroscan⁵ and fatty liver index⁶) and serum biomarkers related to lipids, uric acid and liver function.

3 INVESTIGATIONAL PLAN (brief overview)

3.1 Study Design

- This exploratory and feasibility study is an intervention study assessing the effects of fructose on liver fat accumulation. The study design is described below.

3.2 Allocation to Treatment Groups and Blinding (if applicable)

- We will allocate participants to high and low genetic risk groups

3.3

Study Duration, Enrollment and Number of Subjects

- The study has three phases. First phase will have 200 participants who will visit Human Research Core clinical suite and spend about 30 minutes providing saliva sample and completing a brief questionnaire.
- Second and third phases will have 48 participants. They will first undergo a MRI scan and next day a 3 hour acute fructose challenge (total time 3.5 hours) and then will consume sugar drink as given to them. They will visit again at the end of week 3 for further biomarker, MRI scan and fibroscan measurements.

3.4

Study Population

- Inclusion criteria: Caucasian children and young adults, overweight/obese, ages between 12 and 40 years and no history of alcohol abuse (> 7 drinks per week for a year) and no history of excessive fructose intake (> 14 drinks per week for a year). We will conduct a spot glucose check using a glucometer (Accu-Chek, Roche Diagnostics, CH) to check that the glucose levels of the participants are in the normal range (fasting < 100mg/dl, post meal < 140 mg/dl and random < 200 mg/dl).
- Exclusion criteria includes ages < 12 and > 40 years, healthy weight or morbidly obese, known alcohol abuse, not of Caucasian ethnicity, pregnancy, lactation, glucose levels > 100 mg/dl if fasting, > 140mg/dl if within 2 hours post meal and > 200 mg/dl if random, baseline MRI scan of liver fat fraction > 5%²⁷, and known diagnosis of diabetes, fructose intolerance and chronic kidney disease, use of lipid or uric acid lowering medications.

4

STUDY PROCEDURES (what will be done)

4.1

Screening/Baseline Visit procedures

Phase 1: Recruitment and screening of participants:

Screening: We will recruit 200 Caucasian children and young adults fulfilling our inclusionary criteria: ages between 12 and 40 years, overweight or obese, no history of fructose intake > 14 drinks per week and alcohol abuse (> 7 drinks per week for a year). Height will be measured to the nearest 0.1 cm by a stadiometer situated against the wall in an upright standing position. Height and weight recorded will be used to calculate BMI as kg/m². We will match all participants for BMI (25kg/m² -32kg/m² or 85th-99th percentile).

We will conduct a spot glucose check using a glucometer (Accu-Chek, Roche Diagnostics, CH) to check that the glucose levels of the participants are in the normal range (fasting < 100mg/dl, post meal < 140 mg/dl and random < 200 mg/dl). The exclusion criteria includes ages < 12 and > 40 years, known alcohol abuse or fructose intake > 14 drinks per week, not of Caucasian ethnicity, glucose levels > 100 mg/dl if fasting, > 140mg/dl if within 2 hours post meal and > 200 mg/dl if random, and known diagnosis of diabetes, fructose intolerance and chronic kidney disease.

We will collect saliva from the eligible 200 children and young adults, extract DNA and genotype 10 SNPs shown in Table1.

Genotyping: SNPs will be genotyped from DNA extracted from saliva. Genotyping will be conducted in [name] lab using TaqManSNP genotyping assays (Applied Biosystems, Foster City, CA). The minor allele frequencies (MAFs) of these SNPs range between 7 and 49% based on Caucasian ethnic background. Therefore we are confident about finding 48 individuals with all 10 SNPs. If we don't find individuals with the 10 SNPs, we will mine the literature and find more SNPs that have a role in liver lipogenesis.

4.2

Intervention/Treatment procedures (by visits)

Phase2: Selection of 48 participants for the acute fructose challenge and 3-week intervention study:

The risk allele will be defined as the allele that is associated with higher levels of liver lipogenesis or fat as per previously published studies in Caucasians. The number of risk alleles will range from 0 to 20. The SNP will get a score of 2 with two risk alleles, 1 with one risk allele and 0 with no risk alleles. All the score will be added to get a cumulative score between 0 and 20 for 10 SNPs. We will select participants having > 15 risk alleles and < 6 risk alleles for our acute challenge and 3-week intervention study.

Phase 2&3- visit 1- MRI scan: The 48 individuals enrolled will visit the UNC NRI clinical suite run by the Human Research Core. After obtaining consent, they will be taken to the WakeForest Imaging center for baseline MRI scan. Studies have shown that 5-6% of liver fat is considered normal and anything more than that can reflect increased risk for fatty liver. If the MRI report of the participants shows liver fat > 6%, we will consult with the participant (if > 18years) and/or their parents in confidence and explain why they (or their child) cannot continue to

participate and that they should consult with their primary care physician. We will also advise them on diet and lifestyle that they can follow to minimize the risk. If non-liver adverse findings are reported during MRI, we will provide the participant with a letter that they can show to their physician.

Phase 2&3- visit 2- Oral fructose challenge: After their initial anthropometrics and Fibroscan measurements, they will undergo an oral fructose challenge using a protocol used by Hudgins et al¹³. The participants will be provided with a drink consisting of 0.75g/kg fructose + 0.45g/kg glucose dissolved in 24 Oz of water to be consumed within 15 minutes. An average overweight adolescent of 65 kg will consume 48.75g (65 x 0.75g/kg) fructose and 29.25g (65 x 0.45g/kg) of glucose which is similar equivalent to the sugars in two soda cans²⁸.

Blood and urine will be sampled at baseline and 1 and 3 hours after fructose ingestion. During the challenge period, no other beverage (except water) or food will be allowed.

Anthropometric measurements: Height will be measured using a portable stadiometer. Body composition and weight will be measured by bioelectric impedance technology using the Tanita Dual Frequency total Body composition analyzer (Tanita Inc., Arlington Heights, IL). Measurements will be conducted in a standing position, with subjects wearing light clothing and without shoes. Height will be measured to the nearest 0.1 cm by a stadiometer situated against the wall in an upright standing position. Height and weight recorded will be used to calculate BMI as kg/m². Waist circumference (WC) will be measured using a stretch-resistance tape at the midpoint between the lower margin of the least rib and the top of the iliac crest to the nearest 0.1 inch. Waist and hip circumferences will be measured to the nearest cm in a standing position. Sitting blood pressure (systolic and diastolic blood pressure) will be measured three times using the Omron digital blood pressure monitor (HEM907XL, Omron Healthcare Inc, Lake Forest, IL). The means of these measurements will be used for analysis. Well trained personnel in the UNC NRI Human Research Core will administer questionnaires as well as measure anthropometrics, by one staff member to minimize measurement variation and margin of error.

Questionnaires: The following six sets of questionnaires will be administered to the study participants.

- Personal Interview Form: Information related to demographics
- Medical History: Information related to medical conditions, procedures and surgeries
- Modifiable activity form: Information related to physical activity, sedentary time and job activities
- Medications: Information related to prescription, non-prescription and traditional medications
- Dietary data: Combination of diet recall and food frequency questionnaire will be used to obtain detailed dietary data.

Sample preparation: A total of 24 mL of blood will be drawn at fasting at baseline, 1 hour, 3 hours, at weeks 0 and 3 by a trained phlebotomist through venous puncture. After centrifugation, the serum and plasma fractions of the blood samples will be aliquoted and stored at -80°C to measure the biomarkers listed below using standard reference procedures. All samples will be labeled and inventoried as per standard protocols. Urine will be collected at the same points as blood samples collected at baseline, 3 hour at weeks 0 and 3 will be stored at -80°C. The Human Research Core will assist with phlebotomy services

Meals: All participants will be provided standardized meal for the evening prior to participation of part 1 of phase 2.

Assessment of liver fat accumulation and stiffness: Magnetic resonance imaging (MRI): We will assess liver fat accumulation at week 0 and week 3 using the 2012 Siemens MAGNETOM Skyra 3T MRI system available at the WakeForest Translational Imaging program. If the liver fat fraction >5%¹⁰ then we will exclude the participant from further participation in the nutrient challenge.

Transient elastography: We will use transient elastography to ascertain the changes in the amount of fat in the liver. Transient elastography using a **Fibroscan®** is a non-invasive method of assessing fat accumulation in liver and liver stiffness and works on the principle of vibration controlled transient elastography⁵. A vibration of mild amplitude and low frequency is transmitted through the intercostal space using a vibrator at the skin surface. The vibration induces an elastic shear that propagates through the hepatic tissue. Using pulse echo ultrasound acquisition, the velocity of the shear wave can be determined. The shear wave, directly related to tissue stiffness and expressed in kilopascal (kPa), can be a helpful aid to clinically manage patients with liver disease. The UNC Human Research Core houses a Fibroscan and its trained technicians will help with its use for this study.

Medical care: According to the CDC report (cdc.gov/nutrition/data&statistics), ~51% of Americans drink at least one soda or other type of sugar-sweetened beverages on a given day. Higher prevalences have been found in Southern states and in adolescents. Therefore, we don't anticipate any medical issues as three sugar drinks per day is conforming to the present frequency. However, we will refer to our resident clinician in case any participant wants to consult or has concerns. The participant will be free to withdraw anytime during the study with no repercussions.

Dietary compliance: Dietary compliance will be assessed by the use of frequency questionnaires and three 24-hour diet recalls (Phases 1, 2 and 3).

Dietary guidance: Since each participant will take daily ~500 Kcal more than their normal daily dietary Kcal, we will provide guidance and options on how to cut down ~500 Kcal from elsewhere in their diet, especially in their consumption of sugary drinks.

Biochemical phenotyping: Liver function markers (alanine transaminase (ALT), aspartate transaminase (AST), gamma glutamyl transferase (GGT)), uric acid and lipids (triglycerides and total cholesterol, high and low density lipoprotein (HDL and LDL) cholesterol will be measured in serum using standard reference methods via clinical chemistry analyzer. Serum lipids, uric acid and liver function markers will be measured in [name] lab.

A combination of transient elastography (Fibroscan) and serum liver function markers will be used which will increase the accuracy of non-invasive measurement of fat accumulation in NAFLD; and

Fatty Liver Index (FLI) is a surrogate measure for liver fat estimation. The FLI will be computed based on the following equation which was observed to be 84% accurate in liver fat estimation⁶

$$\text{Fatty Liver Index (FLI)} = \left(e^{0.953 \cdot \log_e(\text{triglycerides}) + 0.139 \cdot \text{BMI} + 0.718 \cdot \log_e(\text{ggt}) + 0.053 \cdot \text{waist circumference} - 15.745} \right) / \left(1 + e^{0.953 \cdot \log_e(\text{triglycerides}) + 0.139 \cdot \text{BMI} + 0.718 \cdot \log_e(\text{ggt}) + 0.053 \cdot \text{waist circumference} - 15.745} \right) * 100^6$$

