Specific Aim3: Determine the relationship between markers of DNL, liver fat accumulation and serum concentrations of lipids, uric acid and liver function markers before and after the fructose challenge

- We will measure serum concentrations of liver function markers, lipids and uric acid at week 0 and week 3;
- As in previous aims, data will be analyzed using students T test, and Pearsons correlations.

Subject Population	Inclusion Criteria
key criteria for Inclusion and Exclusion:	
 Subjects between 12 and 40 years No history of alcohol abuse (> 7 drinks per week) History of fructose intake of < 14 drinks per week Caucasian ethnicity BMI > 25kg/m² – 32kg/m² or 85th -99th percentile but otherwise healthy
	Exclusion Criteria
	
 ages < 12 and > 40 years Pregnant/lactating known alcohol abuse or fructose intake > 14 drinks per week not of Caucasian ethnicity glucose levels > 100 mg/dl if fasting, > 140mg/dl if within 2 hours post meal and > 200 mg/dl if random sample taking anti-hypertensive, anti-diabetic, uric acid and/or lipid-lowering medications known diagnosis of diabetes, fructose intolerance, chronic kidney disease, NAFLD or any liver-related disease, hypertriglyceridemia, polycystic ovary syndrome, hypothyroidism, obstructive sleep apnea, hypopituitarism and hypogandism BMI < 25kg/m² or > 32 kg/m² or < 85th or > 99th percentile Liver fat fraction >5% as per baseline MRI scan
Number Of Subjects	200 for first phase and 48 for the second and third phases
Study Duration	The first phase will be about 30 minutes and the second and third phase will be divided into two visits. Both visits in both phases will be about 3.5 hours each.
Study Phases	(1) Screening: We will screen participants for eligibility to participate in the study based on the inclusionary/exclusionary criteria specified above. The 200 children and young adults selected to participate will provide saliva which will be used to extract DNA and then genotype 10 SNPs. These SNPs are selected based on their association with de novo lipogenesis (DNL) or liver fat accumulation in previously published studies in Caucasians. We will select 12 children and 12 young adults with more than 15 risk alleles and 12 children and 12 young adults with less than six number of risk alleles.
Screening	
Study Treatment	
Follow-Up	

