6.4 Sample Size and Power

Although our sample of 48 may not have the power to detect significant effects of fructose on liver fat, this group of 48 well-characterized individuals, focusing only on one ethnicity and one body weight group and specific genotypes will reduce variability and will generate meaningful data. We expect to apply these approaches and use these data to estimate sample size for larger studies with significant power to detect the effects of gene-nutrients interactions on NAFLD and other metabolic disorders.

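### The BMI matching claimed in section 4.1 is only a shared entry range, so BMI balance between the risk groups is not assured, and the BMI criteria do not say which ages each scale covers

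*Combined protocol and SAP*

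**What the plan says.** **Matching.** Section 4.1 (Screening/Baseline Visit procedures) says "We will match all participants for BMI", followed by a bracket giving 25-32 kg/m² or the 85th-99th percentile. The bracket repeats the synopsis entry criterion. No section gives a pairing rule, a caliper or a frequency-balance rule for BMI.

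**Selection of the 48.** Section 4.2 selects on the risk-allele score alone. The synopsis (Study Phases) adds a split of 12 children and 12 young adults in each risk group. BMI plays no further part once a participant has passed screening.

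**Analysis.** The synopsis (Study Design) compares the two groups with an unpaired t test. Section 6.3 adds paired t tests and repeated measures regression for week 0 against week 3, and a linear regression of AUC for the acute challenge. Neither place names BMI or the child/young-adult stratum as a term. The only covariate named anywhere is concomitant medication (section 4.5).

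**BMI criteria.** The synopsis inclusion list reads "BMI > 25kg/m² – 32kg/m² or 85th -99th percentile but otherwise healthy" and the exclusion list reads "BMI < 25kg/m² or > 32 kg/m² or < 85th or > 99th percentile". Neither attaches an age to either scale. Section 3.4 excludes on weight in words without limits, and the exclusion list under section 4.1 omits BMI.

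**Use made of the restriction.** Section 6.4 argues that "focusing only on one ethnicity and one body weight group and specific genotypes will reduce variability".

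**The concern.** The primary objective in section 2.2 is a genetic-specific effect on liver fat, so the comparison that matters is change in the high-risk group against change in the low-risk group. Those groups are defined by genotype and are not randomised. A reader told that participants are matched for BMI would take BMI as controlled between them, when the design only confines everyone to the same range.

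BMI is not a neutral characteristic in this plan. The drink is scaled to body weight, so at equal height a participant at 32 kg/m² receives 32/25 = 1.28 times the daily sugar of one at 25 kg/m². BMI is also a term in the Fatty Liver Index, which section 6.1 lists within the main outcome.

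The second issue is eligibility. Joining the two BMI scales with an unqualified "or" in both lists leaves staff without a stated rule for adolescents. The missing age boundary also leaves the 12-per-cell quotas undefined at the margin.

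**Working it through.** The plan gives no BMI-balance or power figure to reproduce. Three checks apply.

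**1. Do the BMI lists agree with each other?** Let A = inside 25-32 kg/m² and B = inside the 85th-99th percentile. Inclusion is A or B. Exclusion is not-A or not-B.

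| A | B | Included | Excluded |
|---|---|---|---|
| yes | yes | yes | no |
| yes | no | yes | yes |
| no | yes | yes | yes |
| no | no | no | yes |

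Anyone who meets exactly one range is both included and excluded. If A is applied only to adults and B only to children, the two middle rows cannot arise and the conflict disappears.

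**2. How far apart could mean BMI be by chance?** Inputs: 24 per risk group and 12 per cell (synopsis); range 25-32 kg/m² (section 4.1). Assumption: BMI uniform over that range.

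- SD = 7/√12 = 2.02
- SE of the difference = SD × √(2/n)
- n = 24: SE = 2.02 × √(2/24) = 0.58; 95% range ±1.96 × 0.583 = ±1.14 kg/m²
- n = 12: SE = 0.825; 95% range ±1.62 kg/m²
- With an assumed SD of 1.5 to 2.5: ±0.85 to ±1.41 at n = 24, and ±1.20 to ±2.00 at n = 12

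A simulation from the uniform distribution gave ±1.14 and ±1.61. Under a normal approximation, the chance of a standardised difference above 0.25 is about 39% at 24 per group and 54% at 12, whatever the SD.

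The width of the range also matters for the plan's own index. Across 7 BMI units the Fatty Liver Index logit moves by 0.139 × 7 = 0.97, an odds ratio of 2.65. Sharing the range does not make participants alike on that index.

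**3. What would adjustment gain?** With correlation r between BMI and liver-fat change, the share of residual variance removed is r². For an assumed r of 0.3 to 0.5 this is 0.09 to 0.25. The standard error falls by a factor of √0.91 = 0.95 to √0.75 = 0.87, that is, by about 5% to 13%. Residual degrees of freedom go from 48 − 2 = 46 to 48 − 4 = 44.

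**The case against.** **Chance imbalance is already in the standard error.** An unpaired comparison allows for it. At the 95% limit above, the shift in the outcome difference is r × 1.14/2.02, or 0.17 to 0.28 outcome SDs for r of 0.3 to 0.5. The standard error is √(2/24) = 0.29 SD, so even that case stays below one standard error. This stands: the figures show a precision loss and an unprotected comparison, and they do not show bias. A systematic BMI difference by genotype cannot be sized from the documents.

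**Age is largely handled by design.** Each risk group has 12 children and 12 young adults, so child/adult status is balanced at enrolment. This stands. Leaving the stratum out costs precision only; age within stratum remains open.

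**The eligibility contradiction is only literal.** A reader might infer that the criteria demonstrably admit and reject the same adolescents. The documents do not support that. The usual adult/child reading removes the conflict, and the number of adolescents inside one range only would need growth-chart values that the plan does not give. The defect is an unstated age rule.

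**Inconsistent admission between sites or risk groups.** This too might be inferred. The plan describes one screening location, with the second centre used for imaging, and BMI is settled before genotyping. Ambiguous admission should therefore not favour either risk group.

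**Eighteen-year-olds falling in neither group.** Section 4.2 says "we will consult with the participant (if > 18years) and/or their parents in confidence", which might be read as a stratum boundary. It concerns only who is told of a high MRI result. The synopsis rationale and section 1 refer to young adults as 18-39 years when citing prevalence. That hints at 18 but is not a study definition, and the study runs to 40.

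**Section 6.4 does not rely on matching.** Correct. It claims that restriction reduces variability, which is a fair description of what the entry range does.

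**Conclusion.** The point holds in a limited form. Section 4.1 uses the word match for what is a restriction; nothing pairs or balances the risk groups on BMI, and the stated between-group test adjusts for neither BMI nor the selection stratum. BMI balance is not assured. It would go too far to say that the groups will be unbalanced or the comparison biased, since the common range limits the difference and the groups may turn out similar.

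The ±1.14 kg/m² rests on a uniform 25-32 kg/m² spread, which would not describe children admitted by percentile, so for the mixed groups of 24 it is only illustrative. The 9-25% variance reduction rests entirely on an assumed correlation.

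The BMI criteria conflict as written and need an age rule. The effect on who is enrolled cannot be quantified from the documents.

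The study is exploratory and section 6.4 disclaims power, so the consequence is moderate. It still deserves correction because section 6.4 also says these data will be used to size larger studies, and the remedy uses data already collected.

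**What to change.** 1. In section 4.1, replace the claim of matching with a statement that entry is restricted to the stated BMI range.
2. Reconcile the BMI criteria in the synopsis, section 3.4 and section 4.1. Keep the existing limits, say in both the inclusion and exclusion lists which age stratum each applies to, and state the age boundary used for the 12-per-cell quotas.
3. Compare week 0 to week 3 MRI liver-fat change between risk groups with a linear model containing risk group, the child/young-adult stratum, and baseline BMI standardised within stratum (for example a within-stratum z-score). Standardising avoids forcing one slope across kg/m² and percentile scales.
4. Report baseline BMI by risk group, within stratum.

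The cost is wording changes in those places and two degrees of freedom out of 48. BMI and the stratum are already recorded at screening. If BMI turns out to be unrelated to liver-fat change, the BMI term gains nothing.

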Safety Evaluations	
At screening, to check for blood glucose values, we will conduct a spot glucose check using a glucometer (Accu-Chek, Roche Diagnostics, CH) to check that the glucose levels of the participants are in the normal range (fasting < 100mg/dl, post meal < 140 mg/dl and random < 200 mg/dl). Secondly, we will have a physician who will be available if needed. We will also conduct pregnancy test if needed.
 
Also, we will exclude participants for further participation if we find that the participant has high liver fat fraction (>5%) during our baseline MRI scan¹⁰. The participant will be given a report that they can show to their physician for treatment.

Statistical And Analytic Plan	Our main outcome measure is change in liver fat via MRI scan, fatty liver index equation and through fibroscan measurements. We will also measure serum concentrations of other lipids, liver function markers and uric acid. Data will be assessed using descriptive measures and confidence intervals. Paired t-tests and repeated measures regression analysis will be performed to explore the significant differences between week 0 and week 3.
DATA AND SAFETY MONITORING PLAN	A data and safety monitoring plan will be instituted for this study that will ensure adherence to the protocol approved by UNC IRB. [name] (PI) and co-investigators will review the phenotype and genotype data as they are generated. Any adverse event that is reported to either the principal investigator or her designated research associates by the subject or medical staff caring for the subject and which meets the criteria will be documented as such. Any event that is reported will then generate an adverse event report, which will be submitted to the IRB. The report will include a description of the event, when and how it was reported, as well as any official chart records or documentation to corroborate the event or the reporting of the event

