1.3 Non-Clinical and Clinical Study Findings

There are no immediate benefits. In long-term, we can provide genetic risk-guided diet plans to individuals who may be at high risk.

Risks: We don't anticipate major risk since we will exclude individuals who are diabetic, pre-diabetic, have high liver fat at baseline and are at high risk for these and other metabolic diseases. The only risk can be weight gain. We will advise on cutting calories elsewhere in their daily diet. We will also advise the participants to avoid fruit juices and other sodas for the duration of 3 weeks.

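### Section 1.3 rests its low-risk statement on excluding pre-diabetic people, but the single spot-glucose screen, which need not be fasting and accepts a 'random' reading up to 200 mg/dl, does not deliver that exclusion

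*Combined protocol and SAP*

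**What the plan says.** Section 1.3 gives the reason for anticipating no major risk: "we will exclude individuals who are diabetic, pre-diabetic, have high liver fat at baseline", together with others at high metabolic risk.

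The operative criteria are in the Synopsis (Subject Population) and in sections 3.4 and 4.1. Sections 3.4 and 4.1 exclude a "known diagnosis of diabetes, fructose intolerance and chronic kidney disease". The Synopsis list is longer, beginning "known diagnosis of diabetes, fructose intolerance, chronic kidney disease, NAFLD or any liver-related disease", and it also excludes anti-diabetic medication. None of the three lists names pre-diabetes.

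Glycaemia is tested once. The Synopsis (Safety Evaluations) states: "At screening, to check for blood glucose values, we will conduct a spot glucose check using a glucometer". The stated purpose is "to check that the glucose levels of the participants are in the normal range", and the accepted values are "fasting < 100mg/dl, post meal < 140 mg/dl and random < 200 mg/dl". The matching exclusion reads "glucose levels > 100 mg/dl if fasting, > 140mg/dl if within 2 hours post meal and > 200 mg/dl if random".

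Fasting is mentioned for the blood samples of the intervention phase. Section 4.2 (Sample preparation) says: "A total of 24 mL of blood will be drawn at fasting at baseline, 1 hour, 3 hours", at weeks 0 and 3. The serum analytes listed in section 4.2 (Biochemical phenotyping) are liver enzymes, uric acid and lipids. Glucose is not among them.

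**The concern.** A risk statement that depends on an exclusion is only as good as the rule that carries the exclusion out. Here no diagnosis criterion covers pre-diabetes, so everything depends on the spot reading. How strict that reading is depends on the state in which the person happens to be sampled, and the plan does not fix that state.

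The first consequence concerns safety. Everyone selected, including children from age 12, takes the challenge drink and then one drink a day for three weeks. The people whom section 1.3 describes as excluded could be among them.

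The second is scientific and smaller. Section 6.4 concedes that 48 participants may give too little power and relies on a well-characterised, narrow sample to limit variability. A glycaemic entry rule that varies with appointment time works against that aim.

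**Working it through.** The plan states no figure to reproduce. The check applies the rules as written and then looks for anything else that would close the gap.

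**1. The limits as written** (Synopsis, sections 3.4 and 4.1), applied to a range of readings:

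| Reading (mg/dl) | Classed fasting | Classed post meal | Classed random |
|---|---|---|---|
| 99 | accepted | accepted | accepted |
| 110, 125, 139 | excluded | accepted | accepted |
| 150, 180, 199 | excluded | excluded | accepted |
| 201 | excluded | excluded | excluded |

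Readings of exactly 100 (fasting), 140 (post meal) and 200 (random) are neither accepted nor excluded, because one rule uses 'less than' and the other 'greater than'. All accepted values carry the same normal-range label.

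**2. Which column applies to a non-fasting sample.** The two rules differ.

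- Exclusion wording: post meal means within two hours. A non-fasting sample taken later has only the random class left. The limit then moves from 140 to 200, a step of 200 − 140 = 60 mg/dl, and it loosens as time since eating increases.
- Acceptance wording: post meal has no time bound. A sample taken three hours after a meal could still be post meal, with a limit of 140. What is left for 'random' is then unclear, since the term is defined nowhere.

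On either reading, a sample recorded as random passes up to 200.

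**3. Whether the sampling state is fixed.** Section 3.3 describes the Phase 1 visit as about 30 minutes, with saliva and a brief questionnaire. It does not mention glucose. The Synopsis (Safety Evaluations) and section 4.1 place the reading at screening. No section asks participants to fast for it or says which state must be used.

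**4. Whether a later step closes the gap.** Between screening and the challenge drink the plan has genotyping, the baseline MRI, anthropometrics, Fibroscan and the baseline blood draw. The draw is fasting, but glucose is not a listed analyte. No second glucose check is stated.

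**5. Exposure after entry.** Section 4.2 uses a 65 kg example: 65 × 0.75 = 48.75 g fructose and 65 × 0.45 = 29.25 g glucose, together 78 g per drink. Section 7 gives one drink daily for three weeks, so 21 × 78 = 1,638 g, in addition to the challenge drink.

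**The case against.** Several points on the other side have force.

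- **Different limits for different states are not an error in themselves.** This stands. A reader might infer that the limit doubles from 100 to 200, but that comparison puts fasting and fed readings on one scale. Only the 140-to-200 step is anomalous, and it depends on the exclusion wording.
- **A definite example is not secure.** A reader might infer that someone at 185 mg/dl three hours after lunch is plainly eligible. The acceptance wording sets no time bound on post meal, so the same person could fail the limit of 140. The documents support only that the outcome is undetermined.
- **Pre-diabetes is not defined.** This stands. Calling a person with a given random value pre-diabetic needs a standard that the documents do not give. The inconsistency therefore rests on the plan's own fasting limit, its own normal-range label and its own claim in section 1.3.
- **The lack of a fasting requirement is inferred from silence.** This stands as a limit on the claim. Anyone who happens to be sampled fasting meets the tighter limit.
- **Other criteria narrow the pool.** The Synopsis also excludes hypertriglyceridemia, polycystic ovary syndrome, sleep apnea, known NAFLD, BMI above 32 and liver fat above 5%. These may remove some at-risk people, but none measures glucose. The 'otherwise healthy' wording and the medical history form could surface a known diagnosis, but not an unknown one.
- **The exposure is modest and mitigated.** The drink is described as equal to two sodas, participants are advised to cut calories elsewhere, and a physician is available. This tempers the harm but does not supply the missing exclusion.

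**Conclusion.** The mismatch holds. Section 1.3 relies on an exclusion that no criterion names and that the only glycaemic test, as written, does not deliver for people screened non-fasting. The ambiguity over 'random' and over the two post-meal wordings adds to it.

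In the rule itself, the size is a 60 mg/dl step on the exclusion wording and acceptance of any reading below 200 that is recorded as random. The number of people is unknown: the documents give no prevalence of pre-diabetes and no distribution of sampling states. The finding shows that such people are not reliably kept out, not that any will be enrolled.

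A reader might also infer that undetected cases would fall unevenly between the high and low genetic risk groups and bias their comparison. Nothing in the documents shows this, and it forms no part of the conclusion.

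The conclusion assumes that silence on fasting at screening means fasting is not required, and that no unstated glucose check precedes the drink. It warrants a correction before enrolment, mainly because a stated ground for safety is not met and the remedy is cheap.

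**What to change.** Reconcile section 1.3 with the glucose criteria in the Synopsis (Subject Population and Safety Evaluations) and in sections 3.4 and 4.1, using the same text in each. Define 'random', align the two post-meal wordings, and say what happens at exactly 100, 140 and 200. Then choose one of two routes:

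1. **Make the check capable of delivering the exclusion.** One example is to use the fasting state already planned at the week 0 visit, before the drink is given. The investigators should decide which limit governs and write it down, together with what they mean by pre-diabetic.
2. **Keep the screening check as it is**, remove 'pre-diabetic' from the basis of the risk statement in section 1.3, and restate the risk accordingly.

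The second route costs only wording. The first adds one glucometer reading per participant at a visit where fasting blood is already drawn. Its downside is a few late screen failures, after genotyping and MRI have been paid for. The cells hold 12 people each, chosen for extreme allele counts, so each loss is 1/12, or about 8% of a cell, and may be hard to replace.
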